6.4.1 Analysis of Primary Efficacy Endpoint

The primary efficacy endpoint is change from baseline to week 12/EoT in mean micturitions per 24 hours in children (5 to <12 years of age).

6.4.1.1 Primary Analysis for Primary Efficacy Endpoint

The primary estimator for the primary estimand as defined in Section [2.1.1 Estimand] will be calculated according to the evaluation of the primary efficacy endpoint. The primary efficacy endpoint will be analyzed using an analysis of covariance (ANCOVA). The ANCOVA model will include treatment group, sex and geographical region as fixed effects and the mean number of micturitions per 24 hours at baseline as covariate. This analysis will be performed with imputation of missing visit 7/week 12 data using the last observation carried forward (LOCF) method.

The hypothesis for comparisons is given as follows:

- H₀: The adjusted mean change from baseline at visit 7/week 12 in mean number of micturitions per 24 hours for mirabegron and placebo are the same.
- H1: The adjusted mean change from baseline at visit 7/week 12 in mean number of micturitions per 24 hours for mirabegron and placebo are not the same.

Statistical testing will be done 2-sided at a 10% significance level. A 90% CI for the treatment difference (mirabegron – placebo) will be provided. The primary analysis will use the FAS. The plausibility of the underlying assumption of missing at random for the primary estimator will be evaluated and, therefore, the estimation of the treatment effect.

The ANCOVA model results will be presented with least squares (LS) means and two-sided 90% confidence intervals (CIs) for mean changes from baseline within each treatment group. Differences in LS means between mirabegron versus placebo will be derived and presented together with two-sided 90% CIs. T-statistics corresponding to the Type III sums of squares for the differences in the LS means will be used to obtain p-values for the comparisons.

Model fitting will be visually assessed. A scatter plot of residuals versus predicted values, along with histogram and normal probability plots will be produced.

Sensitivity analyses under alternative assumptions for missing data mechanisms such as missing not at random to show robustness of the estimates will be further specified.

6.4.1.2 Graphical Summary of Data from Primary Efficacy Endpoint

Mean number of micturitions per 24 hours at each visit and change from baseline in mean number of micturitions per 24 hours (without LOCF) will be plotted for FAS: mean (90% CI) values will be presented for each treatment group and visit.

6.4.1.3 Sensitivity Analysis for Primary Efficacy Endpoint

The following sensitivity analyses of the primary efficacy endpoint will be produced.

6.4.1.3.1 Analysis with LOCF for PPS

The same analysis as described in Section 6.4.1.1 will be repeated for PPS (with imputation of missing data, LOCF).

6.4.1.3.2 Analysis without LOCF

The same analysis as described in Section 6.4.1.1 will be repeated for both FAS and PPS, both without imputing for missing data.

6.4.1.3.3 Analysis using Repeated Measures ANCOVA

The primary endpoint will also be analyzed using a repeated measurements analysis of covariance (ANCOVA) model with treatment group, visit (week 2, 4, 8 and 12), sex, geographical region and the interaction between treatment group and visit as fixed effects and mean number of micturitions per 24 hours at baseline as covariate.

An appropriate covariance structure will be selected for the within subject repeated measurements. An unstructured correlation pattern will be used to estimate the variance-covariance of the within-subject repeated measures at first instance. Parameters will be estimated using Restricted Maximum Likelihood with the Newton-Raphson algorithm and using the Kenward-Roger method for calculating the denominator degrees of freedom. If there is a convergence problem due to the unstructured covariance matrix, the unstructured covariance matrix will be replaced by the compound symmetry covariance matrix.

Mirabegron will be compared to placebo using a linear contrast within the repeated measurements ANCOVA model, with 2-sided significance level of alpha = 0.1 and 90% CI.

This analysis will be conducted on the FAS and will serve as a sensitivity analysis to the LOCF method used in the primary model to assess the robustness of the findings.

Model fitting will be visually assessed. A scatter plot of residuals versus predicted values, along with histogram and normal probability plots will be produced.

6.4.1.3.4 Nonparametric Analysis

A nonparametric ANCOVA on rank-transformed data (changes from baseline) will be performed (stratified rank ANCOVA) (with LOCF). Statistical hypothesis testing (p-values) will be performed: the p-value of the treatment difference will be assessed using a rank ANCOVA stratified by region.

Ranks within each geographical region will be derived across the two treatment groups for the baseline value and the change from baseline value.

Then separate linear regression models for each geographical region will be performed with response variable ranked change from baseline value and dependent variables sex and ranked baseline value.

Finally, the stratified mean value test, using the values of the residuals from the regression analysis as scores and geographical region and sex as stratum, compares the two treatment groups using the Cochran-Mantel-Haenszel (CMH) statistics.

Appendix 9.1 present an example of the SAS[®] code to perform this analysis.

In addition, a (nonparametric) estimate for the difference between placebo and mirabegron, with associated (asymptotic) 90% CI, according to Hodges-Lehmann and Moses, will be presented.

These analyses will be conducted on the FAS.

6.4.1.3.5 Sensitivity Analysis for the Primary Estimand

Two analyses of the primary endpoint will be performed where missing data will be imputed using multiple imputation obtained from the procedure MI from SAS®.

The imputation process will be broken up into a sequence of multiple imputation steps using PROC MI. Two different sensitivity analyses will be performed by following either steps 1, 2a, 3, and 4 (missing not at random), or steps 1, 2b, 3, and 4 (missing at random):

- Step 1: Subjects who have missing values for intermediate visits, the missing data will be imputed using the Monte Carlo Markov Chain (MCMC) methodology, as available in PROC MI and option MCMC. The results of this procedure will be stored in a dataset. This dataset now contains a so-called monotone missing data pattern (i.e., for a subject with missing data, all values are missing after a certain time-point). It is assumed here that subjects with missing data follow the same model as other subjects in their respective treatment arm that have complete data. It can be said that this is a reasonable assumption for this partial imputation process because subjects tend to miss intermediate visits due to scheduling conflicts or other reasons unrelated to their medical condition under study.
- Step 2a: sequentially for one time-point data will be imputed for missing values: first for week 2 -> week 4 -> week 8 and finally for week 12. Missing data will be multiple imputed under a missing not at random assumption: borrow information from placebo arm subjects. When imputing missing values for week t (t = 2, 4, 8, 12), the input dataset will include data from all placebo subjects and only data from those subjects from the mirabegron arm that have missing values at week t (Go to step 3.).
- Step 2b: sequentially for one time-point data will be imputed for missing values: first for week 2 -> week 4 -> week 8 and finally for week 12.
 Missing data will be multiple imputed under a missing at random assumption: borrow information from patients in the same treatment arm. When imputing missing values for week t (t = 2, 4, 8, 12), the input dataset will include data from all subjects and only data from those subjects from the placebo and mirabegron arm that have missing values at week t.
- Step 3: Perform ANCOVA on each of the imputed datasets at week 12.
- Step 4: Results from ANCOVA analysis on the imputed datasets will be combined to derive an overall result by using PROC MIANALYZE.

These analyses will be conducted for the FAS.

6.4.1.4 Summary by Subject and Caregiver

In this study the eDiary contains an entry to capture whether the caregiver or the subject entered the data.

To investigate whether there is a difference in scoring the micturitions by the caregiver or the subject the mean number of micturitions per 24 hours will be calculated for each of them separately. This will be done as follows: for each (valid diary) day, the number of micturitions entered in the eDiary will be calculated for the subject and the caregiver, separately. Next, for each visit, the mean number of micturitions will be calculated for the caregiver and subject (see Section 5.1).

Presented will be the results for each age group and overall by treatment, visit and caregiver/subject.

Note 1: a diary for a caregiver is valid for an analysis visit when at least 2 valid diary days are available. Same for subject.

Note 2: in the event that 2 or more caregivers enter data in the eDiary of a subject these data will be reported as coming from 1 caregiver.

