5 EFFICACY AND SAFETY ENDPOINTS

Data for the efficacy endpoints will be recorded on an e-diary. This e-diary consists of a:

- 5-day Weekday Diary (bladder diary, Monday Friday), which is used for a 5-day period to record micturition frequency and incontinence episodes, and
- 2-day Weekend Episodic Diary (Saturday and Sunday), which is used to record micturition frequency, incontinence episodes, (pee) volume measurements, and worst leakage severity.

A valid diary day for:

• "Volumes"

In the 2-day Weekend Episodic Diary, is any e-diary day for which at least one "Pee Volume" greater than 0 mL is recorded with complete date and time.

- "Micturitions"
- In 2-day Weekend Episodic Diary, is any diary day for which at least once "Pee Volume" greater than 0 is recorded.
- In 5-day Week Diary, is any diary day for which the response to the question "Number of times using the toilet during the day/night" is not missing.
 - "Incontinence episodes"
- In 2-day Weekend Episodic Diary, is any diary day for which at least:
 - One micturition ("Pee Volume" >0) and
 - One "Leakage" or "Pee in toilet and Leakage" are recorded.
- In 5-day Week Diary, is any diary day for which:
 - The response to the question "How was your day/night" is not missing.

A valid diary for an analysis visit is a diary with at least 4 valid diary days within that analysis visit window. If for more than 7 days the diary is filled in prior to a visit, only the last 7 days prior to that visit will be used for calculation of the efficacy endpoints.

The number of valid diary days: Count of the valid diary days during the 7-day diary period. Days of visits to the clinic will not be counted as valid diary days.

In the event that in the 2-day Weekend Episodic Diary there are two entries with the same collection date and time but with different times of entry on the device, the last entry (time) will be used for analysis.

For several of the secondary efficacy endpoints, diary data will be classified as either "daytime" or "nighttime", where "daytime" is considered to mean "between waking up in the morning and going to sleep later the same day or next day" and "nighttime" means "between going to sleep on a day and waking up on the same or next day".

Whether an entry into the 5-day Week Diary is done during daytime or nighttime is captured on this diary.

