For entries into the 2-day Weekend Episodic Diary, "daytime" and "nighttime" will be derived from the time the subject went to sleep and the time the subject awakened. These times are entered on this diary by the subject.

The go-to-bed time for Sunday is not captured in the diary. In order to distinguish between daytime and nighttime on Sunday the go-to-sleep time will be imputed as occurring a short time after the second (evening) SBPM was performed: time of second SBPM plus 1 hour. If there is no time entered in the diary for the evening SBPM, then the go-to-sleep time will be imputed as 23:59 (on Sunday).

5.1 **Primary Efficacy Endpoint**

The primary efficacy endpoint is the change from baseline to week 12/EoT in mean number of micturitions per 24 hours in children (5 to <12 years of age).

Number of micturitions per 24 hours is calculated from:

• The response to the questions "Number of times using the toilet during the night" and "Number of times using the toilet during the day" on the 5-day Week Diary,

and

• The number of times a "Pee in toilet" or a "Pee in toilet and leakage" was entered into the 2-day Weekend Episodic Diary.

For a weekend day:

- The daytime micturitions will be derived from the number of times a "Pee in Toilet" or a "Pee in Toilet and Leakage" was entered into the 2-day Weekend Episodic Diary between the time the subject woke up (exclusive) and went to sleep (inclusive).
- The nighttime micturitions will be derived from the number of times a "Pee in Toilet" or a "Pee in Toilet and Leakage" was entered into the 2-day Weekend Episodic Diary between the time the subject went to sleep (exclusive) and woke up (inclusive).

The total number of micturitions per weekend day is equal to the total number of times, in the diary, an amount of pee was recorded during daytime and nighttime for that day.

For each subject, the mean number of micturitions at Visit x (x=4, 5, 6, 7), using all available (non-missing) number of micturitions per 24 hours for the valid days in the diary (at least 4 and maximally 7), will be calculated as:

Sum of the number of micturitions (per 24 hours) over the valid diary days prior to Visit x Number of valid diary days

Note:

- If for a week day (Monday Friday):
 - the number of daytime micturitions is missing but the number of nighttime micturitions is not missing then the number of micturitions for that day is considered to be the number of micturitions during the nighttime.

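### The subject-versus-caregiver summary divides a shared day's voids between the two people, so on those days it measures who entered the data rather than who scored differently

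*SAP*

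**What the plan says.** SAP 6.4.1.4 gives its purpose as "To investigate whether there is a difference in scoring the micturitions by the caregiver or the subject". It relies on a diary field: "In this study the eDiary contains an entry to capture whether the caregiver or the subject entered the data". The documents do not say whether that field is filled in for each entry, each form or each day.

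The counting rule is that "for each (valid diary) day, the number of micturitions entered in the eDiary will be calculated for the subject and the caregiver, separately". The daily counts are averaged by visit with reference to SAP 5.1, and results are shown by age group, treatment, visit and reporter. Note 1 sets a lower validity bar than the main endpoint. Here, "a diary for a caregiver is valid for an analysis visit when at least 2 valid diary days are available", and the same applies to the subject; for the efficacy endpoints, "A valid diary for an analysis visit is a diary with at least 4 valid diary days within that analysis visit window". Note 2 pools several caregivers of one child as one caregiver. No rule covers a day on which both child and caregiver made entries, and the section does not say whether each person's denominator is the days with that person's entries or all valid days.

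The data structure allows shared days. Under SAP 5 and 5.1, weekday data are two answers, one for day and one for night, while weekend data are individual episodes. Protocol 7.1.1 and 7.6 let the child or a parent, guardian or caregiver complete the diary, and plan no parallel recording by both.

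**The concern.** A comparison of scoring needs each person's count of the same thing: all voids in 24 hours. The rule gives each person's count of the voids that he or she entered. With no parallel recording, on a shared day these are two parts of one total. The child's part falls as the caregiver's rises, even if both would have counted identically.

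The validity rules do not catch this if they are applied to each reporter. SAP 5.1 lets a lone weekday day or night count stand for the whole day, and SAP 5 accepts a weekend day for micturitions once a single non-zero volume is recorded. A caregiver's one night void could then pass as a 24-hour count of 1.

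At stake is the usefulness of the table. It is the plan's check on whether the reporter matters to how the primary endpoint is measured. As written, it can show a gap where scoring agrees, and it can obscure a real difference on shared days. Because results are shown by visit and treatment, a change over time in who enters the data could look like a change in scoring.

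**Working it through.** SAP 6.4.1.4 states no figure to reproduce, so the check applies its counting rule to constructed diaries.

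**Inputs.** Seven valid days; a true count of 9 voids on every day (8 day, 1 night); identical scoring by both people; reporter recorded for each entry. The 9 is an assumption; Protocol 5.1, inclusion criterion 15, requires an average of at least 8 a day at baseline. Except where stated, the denominator is the number of days with that person's entries.

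**Formula.** Reporter mean = sum of the voids that person entered ÷ number of days counted for that person.

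| Pattern of data entry | Subject mean | Caregiver mean | Gap (subject − caregiver) |
|---|---|---|---|
| A. Child enters the day count, caregiver the night count, all 7 days | 56/7 = 8.0 | 7/7 = 1.0 | 7.0 |
| B. Caregiver enters all weekday data; on each weekend day child enters 3, caregiver 6 | 6/2 = 3.0 | (45 + 12)/7 = 8.14 | −5.14 |
| C. Child enters 5 whole weekdays, caregiver 2 whole weekend days | 45/5 = 9.0 | 18/2 = 9.0 | 0 |
| D. As C, but all 7 valid days as denominator for both | 45/7 = 6.43 | 18/7 = 2.57 | 3.86 |
| E. Caregiver enters everything | no valid diary | 63/7 = 9.0 | none |

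The true reporter difference is 0 throughout. In A and B neither mean equals 9. In C and E each available mean is a correct 24-hour count. D shows that the unstated denominator alone can create a gap, with no shared day at all.

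**General case, every day shared.** If the child enters fraction f of each day's voids, the means are 9f and 9(1 − f), so the gap is 9f − 9(1 − f) = 9(2f − 1):

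- f = 0.1: −7.2
- f = 0.25: −4.5
- f = 0.5: 0
- f = 0.75: +4.5
- f = 0.9: +7.2

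If a child moves from f = 0.5 at one visit to f = 0.75 at the next, the gap goes from 0 to 4.5 with no change in scoring.

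**After the change proposed below.** Pattern A gives 7 mixed days at 9.0 and no reporter comparison. B gives 5 caregiver-only days at 9.0 and 2 mixed days at 9.0. C gives 5 subject-only and 2 caregiver-only days, both at 9.0. E gives 7 caregiver-only days at 9.0. The artificial gap disappears in every pattern.

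**The case against.** The strongest reply is that the problem depends on facts the documents do not give. If the reporter field is filled in once per day, no day is split; Note 1, which counts valid days for each person, can be read as assigning whole days to people. Nor do the documents say how common shared days are. Both points stand, and the conclusion must be conditional on them. They do not remove the problem: the rule counts separately within each day, the diary permits two people to contribute to one day, and nothing says what happens then.

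Several stronger conclusions are tempting, and the documents do not support them:

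- A reader might infer that neither mean is ever a 24-hour count. Patterns C and E show otherwise.
- A reader might infer that the table is bound to show a large gap. The share of mixed days is unknown, and the gap is 0 at f = 0.5.
- A reader might infer that the two means always add up to the true count. In pattern B they add to 3.0 + 8.14 = 11.14, because the denominators differ.
- A reader might infer that no real reporter effect could ever be seen. Single-reporter days still give complete counts.
- A reader might set the gap of 7 against the planned treatment effect of 0.9. The first is a contrast between reporters within one child; the second is a difference between randomised arms. They are not comparable.
- A reader might infer that the primary result is at risk. SAP 5.1 counts voids regardless of who entered them, the ANCOVA in SAP 6.4.1.1 has no reporter term, and SAP 7.1 describes this summary as descriptive.

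It can also be said that no re-labelling yields a clean reporter effect, since child and caregiver do not record the same day independently. That is true, and it limits what the fix can achieve.

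**Conclusion.** The point holds in a limited form. On days when both people enter data, the SAP 6.4.1.4 rule divides one 24-hour total between them, so the per-24-hours label is wrong for those days and the difference reflects data entry rather than scoring. With 9 voids a day, entry-level recording of the reporter and every day shared, the artificial gap is 9(2f − 1): between −7.2 and +7.2 for f from 0.1 to 0.9. These are illustrations of the mechanism, not forecasts, because the share of mixed days and the level at which the reporter is recorded are not stated.

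Days entered by one person are sound provided the denominator is that person's own days; the SAP should say that it is. The consequence is confined to a descriptive table about how the primary endpoint is measured. It is still worth correcting, because on shared days the table cannot answer the question it was added to answer.

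**What to change.** Rewrite the derivation in SAP 6.4.1.4:

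1. State whether the reporter field is recorded per entry, per form or per day.
2. For each valid diary day, compute the full 24-hour count as in SAP 5.1, whoever entered it.
3. Label the day subject-only, caregiver-only or mixed.
4. Summarise the full-day counts by label, with age group, treatment and visit as planned, using only that label's days as the denominator and keeping the minimum of 2 valid days per label.
5. Base the subject-versus-caregiver comparison on single-reporter days and report mixed days separately.

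The cost is one SAP paragraph on the same data; SAP 1 allows revisions before database hard lock. There are downsides. Mixed days give no reporter comparison, so a child whose days are all shared contributes nothing to it. Some days drop out under the 2-day minimum: a diary with 2 subject-only days, 1 caregiver-only day and 1 mixed day keeps only the first label. Differences in which children or which days each person records remain, and the table should carry a note saying so.

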6.4.1.5 Subgroup Analysis for Primary Efficacy Endpoint

For the primary efficacy endpoint, descriptive statistics (n, mean, 95% confidence interval around the mean, SD, minimum, median, maximum) will be calculated for mean change from baseline at each visit by sex, race, ethnicity, geographical region, formulation (tablets vs. oral suspension), prior OAB treatment and symptomatic UTI, using LOCF.

The following interactions will be investigated, separately:

- treatment group by sex;
- treatment group by geographical region;
- treatment group by formulation;
- treatment group by prior OAB treatment; and
- treatment group by symptomatic UTI (yes/no) Note: symptomatic UTI is yes when it is reported as an AE during the trial, irrespective when it occurs.

To investigate the first two interactions, separately, data of the primary efficacy endpoint will be analyzed using an ANCOVA model with treatment group, sex and geographical region as fixed effects, the mean number of micturitions per 24 hours at baseline as covariate and including the, above mentioned, interaction term that is investigated.

To investigate the last three interactions, separately, data of the primary efficacy endpoint will be analyzed using an ANCOVA model with treatment group, sex, geographical region and either formulation, prior OAB treatment, or symptomatic UTI (yes/no) as fixed effects, the mean number of micturitions per 24 hours at baseline as covariate and including the, above mentioned, interaction term that is investigated.

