2.1.3 Summary of Key Safety Information for Investigational Product(s)

Mirabegron has not been approved or marketed for use in pediatric subjects.

Detailed reference safety information (RSI) can be found in the Investigator's Brochure for mirabegron.

- CONFIDENTIAL -

Mirabegron has been approved in more than 81 countries worldwide. In adults, the safety of mirabegron treatment has been well characterized in 5863 subjects (95% with OAB) in the phase 2/3 registration studies treated with mirabegron at doses ranging from 25 to 200 mg once daily. Identified risks include increased heart rate and tachycardia, hypersensitivity reactions, increased blood pressure and urinary retention. Potential risks include QT prolongation, urinary tract infection (UTI), fetal disorders after exposure during pregnancy and events induced by concomitant treatment with cytochrome P450 2D6 (CYP2D6) substrates with a narrow therapeutic index. The risks of QT prolongation, increased heart rate or increased blood pressure are greater with increasing exposure at supratherapeutic doses and can be mitigated with optimal dose selection. The maximum therapeutic dose of mirabegron based on the overall benefit-risk is 50 mg once daily in adults.

ISN/Protocol: 178-CL-204

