2.3 Risk-Benefit Assessment

This study will be conducted as a double-blind, randomized, multicenter, parallel group, placebo-controlled sequential dose titration study in pediatric subjects from 5 to < 18 years of age with OAB.

The study design and dose rationale are presented in [Section 4 Study Design and Dose Rationale].

Mirabegron tablets have been approved for the indication of OAB in adult subjects. Mirabegron oral suspension has been shown to be safe and well tolerated in 2 phase 1 studies in healthy adult subjects (Studies 178-CL-201 and 178-CL-208). In the pediatric phase 1 studies executed thus far, mirabegron tablets and mirabegron oral suspension had an acceptable safety profile and were well tolerated. Given the available data on mirabegron in the adult population and in the pediatric population to date, the risk-benefit attributes are well defined and can be managed through ongoing safety assessments throughout study conduct as defined in the Schedule of Assessments [Table 1].

The important identified and potential risks in adults are recognized as potential drug safety risks for this study (Study 178-CL-204). These risks will be monitored on a regular basis and can be mitigated as follows:

 The initial dose of mirabegron will be based on the subject's body weight and is predicted to achieve plasma concentrations equivalent to the steady-state exposures Sponsor: APGD ISN/Protocol: 178-CL-204 EudraCT number 2016-001767-37

- CONFIDENTIAL -

expected with 25 mg mirabegron administered once daily in adults (PED25). This low dose is chosen considering possible beta-adrenergic side effects of mirabegron.

- At visit 5/week 4 (i.e., after 4 weeks on PED25), dose up-titration to PED50 will be performed unless the investigator determines that the subject is adequately treated for OAB at the PED25 dose or if there are safety concerns identified and considered associated with the use of PED25. Dose down-titration from PED50 to PED25 can be done at any time thereafter for safety reasons. By striving to get an efficacious dose of mirabegron early after start of dosing, the risk for bladder and kidney damage is mitigated.
- Potential fetal disorders after exposure during pregnancy is mitigated by the inclusion criteria
- Hypersensitivity reactions (immediate or nonimmediate and cutaneous or noncutaneous) will be monitored by AE monitoring and will require discontinuation of study treatment

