9.4.1.3 Subgroup Analysis

For the primary efficacy endpoint, descriptive statistics (n, mean, 95% confidence interval around the mean, SD, minimum, median, maximum) will be calculated for mean change from baseline at each visit by sex, race, ethnicity, geographical region, formulation (tablets vs. oral suspension), prior OAB treatment and symptomatic UTI.

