2.1.1 Estimand

The estimand of most clinical importance for this study is defined by the following four attributes:

- Target population: all children who took at least 1 dose of the study drug, and in whom a non-missing measurement for micturition frequency at baseline and after administration of the study drug is available
- Outcome measurement: micturition frequency/day (24 hours)
- Intercurrent events:
 - 1. Discontinuation from treatment (if week 12/EoT not obtained)
 - 2. AE Urinary Tract Infection (UTI) (if occurred in week 12/EoT)
 - 3. Other muscarinic antagonists or botulinum toxin (if taken during the last 2 weeks prior to week 12/EoT assessment);

In all cases, a hypothetical strategy will be applied.

• Population-based summary: Change from baseline to week 12/EoT in micturition frequency/day (= primary endpoint, primary estimator), compared to placebo.

For this placebo-controlled study, this "de jure" estimand is considered the appropriate choice. As some effect is expected early in the study and with continued treatment could be expected to be maintained, it is considered appropriate to impute for subjects with missing values at visit 7/week 12/EoT by their last recorded post baseline visit value prior to it. This strategy also assumes that the responses after the intercurrent event would be same as for those patients continuing on their respective treatment.

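### The treatment-by-symptomatic-UTI interaction test rests on a flag that can be set after randomisation, even after the week 12 diary, so it may be biased and is too imprecise to inform

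*SAP*

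**What the plan says.** Protocol 9.4.1.3 asks for descriptive statistics on the primary endpoint by several subgroups, ending with "formulation (tablets vs. oral suspension), prior OAB treatment and symptomatic UTI". It gives no timing rule for UTI and no interaction test.

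SAP 6.4.1.5 keeps those summaries, at each visit and with LOCF, and adds interaction models. One is "treatment group by symptomatic UTI (yes/no"). The ANCOVA for it contains treatment, sex, region, baseline frequency, the interaction, and "either formulation, prior OAB treatment, or symptomatic UTI (yes/no) as fixed effects". The timing rule is that "symptomatic UTI is yes when it is reported as an AE during the trial, irrespective when it occurs". The section does not warn that this factor, unlike the others listed, can be determined after randomisation.

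Four other places bear on it:

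- Protocol 2.1.3, on safety: "Potential risks include QT prolongation, urinary tract infection (UTI), fetal disorders after exposure during pregnancy". Protocol 2.3 carries the adult identified and potential risks into this study.
- Protocol 7.3.1: adverse event collection starts at consent or assent and ends 30 days after the final dose.
- Protocol exclusion criterion 31: a symptomatic UTI at baseline postpones the visit until it is treated, so a child can be randomised after a screening-period UTI.
- SAP 2.1.1: the estimand lists as an intercurrent event "AE Urinary Tract Infection (UTI) (if occurred in week 12/EoT").

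**The concern.** A subgroup comparison inherits the protection of randomisation only when membership is settled independently of treatment. Sex and prior OAB treatment meet that condition. A flag built from on-study adverse events need not, and here the sponsor itself names the event as something the drug might cause.

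If mirabegron changed who gets a UTI, the UTI-yes children on drug and on placebo would be different kinds of children, and so would the UTI-no children. A difference between strata could then appear with no true effect modification, or a true one could be hidden. SAP 6.4 applies no multiplicity adjustment, and the result would appear beside baseline interactions with nothing to tell the reader that it is of another kind.

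Timing adds a fault that needs no assumption about drug effects. A UTI in follow-up would classify a week 12 value already recorded. In the by-visit summaries, a UTI in week 11 would sort the week 2 and week 4 changes.

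**Working it through.** **1. The plan's own figure.** SAP 3 gives a difference of 0.9, SD 2.3, two-sided alpha 0.10, 80% power and 82 evaluable children per group.

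n = 2 × (1.645 + 0.842)² × 2.3² / 0.9² = 2 × 6.185 × 5.29 / 0.81 ≈ 80.8, so 81 per group by normal approximation. At 82, power is 80.5% (normal) or 80.2% (noncentral t). Allowing 10% non-evaluable, 82 / 0.9 = 91.1, so 92 per group and 184 in total. The stated figures reproduce.

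The overall contrast has SE 2.3 × √(2/82) = 0.36 and 90% half-width 1.645 × 0.36 = 0.59 micturitions per day.

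**2. What the flag can contain.** Read literally, with the collection window in Protocol 7.3.1:

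- UTI in screening, treated before baseline: before randomisation, can count.
- UTI on treatment, before or during the week 12 diary: after randomisation, counts.
- UTI after the week 12 diary, up to 30 days after the last dose: after the outcome, counts.

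One yes category thus mixes a baseline characteristic, a possible consequence of treatment, and an event that cannot have influenced the outcome.

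**3. Precision.** The documents give no UTI rate, so the counts are assumptions. With n UTI children in each arm of 82:

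SE(interaction) = 2.3 × √(2/n + 2/(82 − n)); half-width = 1.645 × SE.

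- n = 2: 2.3 × √(1 + 0.025) = 2.33; half-width 3.8
- n = 4: 2.3 × √(0.5 + 0.0256) = 1.67; half-width 2.7
- n = 8: 2.3 × √(0.25 + 0.0270) = 1.21; half-width 2.0

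Over assumed UTI rates of 3% to 15% (about 2.5 to 12 children per arm), power to detect a true interaction of 0.9 is 13% to 23%.

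**4. Direction and conditions of bias.** A simulation with 4 million children per arm gave every child a true effect of −0.9, so no interaction exists. A latent factor correlated 0.5 with outcome; its correlation with UTI propensity was set to 0, 0.5 or 0.8. UTI had no direct effect on outcome. All these inputs and the rates below are assumptions.

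| UTI rate, placebo / drug | Factor–UTI correlation | Effect, UTI yes | Effect, UTI no | Spurious interaction |
|---|---|---|---|---|
| 5% / 5% | 0.5 or 0.8 | −0.90 | −0.90 | 0.00 |
| 5% / 10% | 0.5 | −1.08 | −0.95 | −0.13 |
| 5% / 10% | 0.8 | −1.18 | −0.98 | −0.20 |
| 3% / 10% | 0.5 | −1.20 | −0.97 | −0.22 |
| 3% / 10% | 0.8 | −1.39 | −1.02 | −0.37 |
| 10% / 20% | 0.5 | −1.10 | −0.99 | −0.11 |
| 10% / 20% | 0.8 | −1.23 | −1.04 | −0.19 |

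With correlation 0, the interaction was zero to within 0.01 at every pair of rates. The overall randomised contrast stayed at −0.90 throughout.

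**The case against.** The strongest reply is that this is one of five exploratory interactions and no conclusion rests on it. That is right about the main results. The primary ANCOVA in SAP 6.4.1.1 contains treatment, sex, region and baseline only, and the futility calculation in SAP 6.9 takes its least squares means and SD from that model. A reader might infer that the UTI factor threatens the primary result or the interim decision; the documents do not support that.

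Bias is also not certain. A reader might infer that adjusting for UTI necessarily distorts the treatment terms. Protocol 2.1.3 lists UTI among potential rather than identified risks. The simulation shows no distortion when UTI rates are equal across arms or when UTI is unrelated to prognosis.

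Two further readings go too far. The flag is not purely post-randomisation, because a screening UTI can count. And the estimand does not treat every on-study UTI as an intercurrent event, only one in week 12/EoT, so the subgroup factor and the intercurrent event overlap without being the same.

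Finally, low precision affects any small subgroup. That is fair: the half-widths assume equal counts per arm, so they measure imprecision and say nothing about the size of bias.

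What survives is that the interaction test presents a mixed-window, possibly treatment-dependent flag as if it were a baseline factor, without a caveat, and adds a p-value that the protocol did not request.

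**Conclusion.** The point holds in a limited form. The UTI strata are not protected by randomisation, and the within-stratum contrasts and interaction may be biased, on two conditions: treatment affects UTI occurrence, and UTI is related to micturition frequency. Under the assumed scenarios where both held, the spurious interaction was 0.11 to 0.37 micturitions per day; the actual size is unknown. The timing fault is unconditional: a UTI after the week 12 diary cannot modify the week 12 effect.

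Even without bias, the test could say little. Its 90% half-width of 2.0 to 3.8, at 8 down to 2 UTI children per arm, compares with 0.59 for the overall contrast. The plan targets no interaction size, so the design effect of 0.9 serves only as a yardstick.

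This is a supportive analysis. The case for acting is that the test can mislead, is unlikely to inform, and is nearly free to remove.

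**What to change.** In SAP 6.4.1.5:

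- Delete the treatment-by-symptomatic-UTI interaction model.
- Keep the UTI summary required by Protocol 9.4.1.3 as descriptive only, and label it as a non-randomised comparison.
- Replace the timing rule so that a child counts as UTI-yes for a given diary only if onset was on or before that diary.
- If an effect-modifier analysis is wanted, define the factor by UTI recorded before randomisation, from medical history or a screening adverse event, where the recorded data allow. Protocol 10.2.2 and 10.2.3 name no specific UTI-history item, and exclusion criterion 10 removes children with chronic or frequent recent UTI, so this factor may be sparse and it answers a different question.

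Moving on-study UTI to the intercurrent-event analysis is not a ready substitute. SAP 6.4.1.1 to 6.4.1.3 handle missing values but give no rule for setting aside diary data affected by a UTI; one would have to be written.

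The cost is SAP wording, which SAP 1 allows to be revised before hard lock. Adverse event onset is already collected, and the protocol-specified subgroup stays. What is lost is the interaction p-value for on-study UTI.
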